### **Immunogenicity (IG) Analysis Sets**

The Immunogenicity prevalence set includes all subjects in the Safety Set with a non-missing baseline IG sample or at least one non-missing post-baseline IG sample.

The Immunogenicity incidence set includes all subjects in the Immunogenicity prevalence set with a non-missing baseline IG sample and at least one non-missing post-baseline IG sample.

A non-missing IG sample indicates a sample that is evaluable and analyzed. Baseline IG sample is the IG sample that was taken before the first administration of MBG453.

### **Subject Classification**

Subjects may be excluded from the analysis populations defined above based on the protocol deviations entered in the database and/or on specific subject classification rules defined in [Table 2-1](#).

**Table 2-1      Subject classification based on protocol deviations and non protocol deviations criteria**

Analysis set	Protocol deviations leading to exclusion	Non protocol deviation leading to exclusion
FAS	No written informed consent for participation in the study	No dose of any component of study treatment
Safety Set	No written informed consent for participation in the study	No dose of any component of study treatment
DDS	No written informed consent for participation in the study	Not enrolled in safety run-in part or not met the minimum exposure criterion or no sufficient safety evaluations in the absence of DLT during the DLT evaluation period

Analysis set	Protocol deviations leading to exclusion	Non protocol deviation leading to exclusion
PK analysis set	No written informed consent for participation in the study	See definition of PK analysis sets
IG analysis set	No written informed consent for participation in the study	See definition of IG analysis sets

## Withdrawal of Informed Consent

Any data collected in the clinical database after a subject withdraws informed consent from all further participation in the study will not be included in the analyses. But samples collected before the subject withdrawal of consent sent but that have not yet been analyzed at the time of the subject withdrawal may still be used for further testing / analysis in accordance with the protocol and the informed consent form. The date on which a subject withdraws consent is recorded in the eCRF.

Additional data for which there is a separate informed consent, e.g., biological sample etc., collected in the clinical database without having obtained that consent or after withdrawal of consent will not be included in the analyses.

### 2.2.1 Subgroup of interest

No specific subgroups of interest will be considered to support efficacy and safety analyses. Exploratory subgroups analyses for either efficacy or safety may be added later and/or handled in separate planning documents (e.g. TFLs).

## 2.3 Patient disposition, demographics, and other baseline characteristics

The FAS will be used for the analyses below. Patient disposition, demographics and other baseline characteristics will be summarized by dose level of MBG453 (400 mg Q4W, 800 mg Q4W) and for all subjects (“All subjects” column).

### 2.3.1 Patient disposition

Number (%) of subjects screened and enrolled will be summarized by country and center. For subjects who are screen failures, the reasons for not completing screening will be summarized based on “Screening Phase Disposition” eCRF.

The number (%) of subjects in the FAS who started treatment, are still on treatment, who entered and discontinued post-treatment follow-up and who discontinued the study after survival follow-up will be summarized together with the respective reasons for treatment/post-treatment follow-up/end of study discontinuation (which corresponds to end of survival follow-up). All disposition information will be listed.

The number (%) of subjects in the FAS with any protocol deviation (PD) will be tabulated by deviation category. COVID-19 related PD will be tabulated separately. All protocol deviations will be listed, together with their relationship to COVID-19 pandemic.

Protocol deviations leading to exclusion from analysis sets will be tabulated separately and the number (%) of subjects in each analysis set will be summarized.

### **2.3.2 Demographic and other baseline characteristics**

Demographic and other baseline data including disease characteristics will be listed and summarized descriptively for all subjects from the FAS.

BMI (kg/m^2) at baseline will be calculated as weight[kg] / (height[m]) using weight at baseline and height at screening. Body Surface Area (BSA) is based on the Mosteller formula described in [Section 2.4.1](#).

Details on AML diagnosis (initial diagnosis, ELN 2017 risk classification ([Döhner et al 2017](#)), current disease status (de novo or secondary) and cytogenetic abnormalities will be tabulated and time since diagnosis will be summarized.

Relevant medical histories and current medical conditions at baseline will be summarized by system organ class and preferred term. Medical history and current medical conditions will be coded using the Medical Dictionary for Regulatory Activities (MedDRA) terminology. The MedDRA version used for reporting will be specified in the CSR and as a footnote in the applicable outputs. Comorbidities at baseline that exclude subjects from receiving intensive chemotherapy (presence of specific cardiac, pulmonary, hepatic or renal comorbidities) will be summarized by age category (<75 years old and  $\geq$  75 years old).

## **2.4 Treatments (study treatment, rescue medication, concomitant therapies, compliance)**

The Safety set will be used for the analyses below and summary tables will be presented by dose level of MBG453 (400 mg Q4W, 800 mg Q4W) and for all subjects (“All subjects” column).

### **2.4.1 Study treatment / compliance**

The duration of exposure to study treatment and to each study treatment component (MBG453, azacitidine and venetoclax) as well as the actual dose intensity, relative dose intensity, doses changes and cycle lengths will be summarized by descriptive statistics.

#### **Duration of exposure**

The duration of exposure (in months) will be summarized for study treatment (combination) and for each study treatment component individually (MBG453, azacitidine and venetoclax) based on summary statistics and categorical analyses (e.g. exposure <1 month, at least 1 month, at least 2 months etc.). Details on start and end dates used for derivations are outlined in [Appendix Section 5.1](#).

#### **Cumulative dose**

For MBG453, the actual cumulative dose in mg is the sum of “dose administered” from the eCRF of all cycles during the exposure to MBG453.

For azacitidine, the actual dose in mg/m^2 in each cycle is the “dose administered” in mg during that cycle divided by the body surface area (BSA) at the beginning of the cycle using the weight measured before the infusion at that cycle. If the weight is not collected at the beginning of the cycle, the weight from the previous visit will be considered. The actual cumulative dose in mg/m^2 is then the sum of all cycles. The following formula is used for BSA:

BSA (m^2) =  $\sqrt{\text{Weight (kg)} * \text{Height at screening (cm)} / 3600}$  (Mosteller formula)

For venetoclax, the actual cumulative dose in mg is the sum of “dose administered” from the eCRF of all cycles during the exposure of venetoclax.

### **Dose intensity and relative dose intensity**

Dose intensity is defined for subjects with non-zero duration of exposure. For subjects who did not take the drug, the dose intensity is by definition equal to zero. The actual dose intensity (computed as the ratio of actual cumulative dose received and duration in days from first to last cycle initiated) and the relative dose intensity (computed as the ratio of actual dose intensity and planned dose intensity) will be summarized for each study treatment component by descriptive statistics. The planned dose intensity for each of the study treatment components is the ratio of planned cumulative dose and duration in days from first to last cycle initiated:

- For MBG453, the planned dose intensity is 400 mg/28 days or 800 mg/28 days,
- For azacitidine, the planned dose intensity is 75 mg/m^2/day which is equivalent to 525 mg/m^2/28 days,
- For venetoclax, the planned dose intensity is 400 mg/day which is equivalent to 11200 mg/28 days when the recommended full daily dose of Venetoclax is 400 mg and without the ramp-up period.

The relative dose intensity is then computed as the ratio of actual dose intensity and planned dose intensity. As example, if a subject received MBG453 at 600 mg Q4W on average throughout the study (instead of the 800 mg Q4W as planned per protocol), the relative dose intensity for this subject is 0.75.

Details on the duration in days from the first to last cycle initiated for the derivation of the dose intensity and the relative dose intensity are provided in [Appendix Section 5.1](#).

Details on the derivation of cumulative dose, dose intensity and relative dose intensity of venetoclax are provided in [Appendix Section 5.1](#).

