6.1.3 Treatment arms/group

6.1.4 Guidelines for continuation of treatment

Per protocol, dose modifications, including dose interruptions, for toxicities are permitted and are outlined in [Section 6.5](#).

For patients who achieve a CR and have received at least 18 cycles of study treatment, treatment with venetoclax and azacitidine may be discontinued at the discretion of the investigator, and the patient continued on study receiving only single agent MBG453.

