12.3 Treatments

The Safety set will be used for the analyses below.

The duration of exposure to MBG453 and to each study drug (azacitidine and venetoclax) as well as the dose intensity (computed as the ratio of actual cumulative dose received and actual duration of exposure) and the relative dose intensity (computed as the ratio of dose intensity and planned dose intensity) will be summarized by descriptive statistics.

Concomitant medications and significant non-drug therapies prior to and after the start of the study treatment will be listed and summarized according to the Anatomical Therapeutic Chemical (ATC) classification system.

The number of subjects with dose adjustments (reductions for azacitidine and venetoclax, interruptions, or permanent discontinuation) and the reasons will be summarized by study drug and all dosing data will be listed.

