## 4. Change to protocol specified analyses

Not applicable.

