### **End date of the last cycle initiated**

The end date of the last cycle initiated is the maximum date between:

- The planned end date (Day 28) of the last cycle initiated when the last non-zero dose of any last component of the study treatment (MBG453 or azacitidine or venetoclax) is administered,
- The actual date of the last administration of a non-zero dose of any last component of the study treatment.

The end date of the last cycle initiated (Day 28 or beyond) will be applicable even if this date goes beyond the data cut-off date (i.e., it should not be truncated to the date of data cut-off).

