## **Duration from first to last cycle initiated to calculate dose intensity and the relative dose intensity**

For the calculation of the dose intensity and relative dose intensity, the duration in days from first to last cycle initiated will be calculated as follow: end date of the last cycle initiated - date of first administration of study treatment (combination) + 1.

Thus, this derivation will be irrespective of date of death or last contact date (i.e., it should not be truncated to the date of death or date of last contact).

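### SAP relative dose intensity divides every drug's dose by the whole regimen's duration, an undeclared departure from protocol 12.3 that mixes permanent stopping of one drug with missed or reduced doses

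*SAP*

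**What the plan says.** SAP 2.4.1 (Dose intensity and relative dose intensity) gives one rule for all three components: actual dose intensity is "computed as the ratio of actual cumulative dose received and duration in days from first to last cycle initiated". RDI is that figure over a planned rate, and the planned rate is fixed: "For MBG453, the planned dose intensity is 400 mg/28 days or 800 mg/28 days", with corresponding 28-day rates of 525 mg/m² for azacitidine and 11,200 mg for venetoclax. Nothing ends the planned rate when a component is stopped for good.

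Appendix 5.1 calculates the duration as "end date of the last cycle initiated - date of first administration of study treatment (combination) + 1". The end date is the later of two dates. One is planned Day 28 of the final cycle started, that is, the cycle "when the last non-zero dose of any last component of the study treatment (MBG453 or azacitidine or venetoclax) is administered"; the other is "The actual date of the last administration of a non-zero dose of any last component of the study treatment". Whichever drug runs longest therefore sets the denominator for all three. The duration is not cut at death or last contact.

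Protocol 12.3 names the duration of exposure to MBG453 and to each of the other study drugs, and in the same sentence has dose intensity "computed as the ratio of actual cumulative dose received and actual duration of exposure".

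Protocol sections 3 and 6.5.3 let patients who cannot tolerate one or two drugs continue on the others. Protocol 6.1.4 adds that, for patients in CR after at least 18 cycles, "treatment with venetoclax and azacitidine may be discontinued at the discretion of the investigator", with MBG453 continued alone.

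SAP section 4, on changes to protocol-specified analyses, reads "Not applicable".

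**The concern.** Once a drug is stopped for good, its numerator is frozen while the shared denominator keeps growing with every cycle of the remaining drugs. RDI for that drug then depends partly on how well doses were delivered while it was given and partly on how long the other drugs went on. One number cannot separate the two.

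This is clearest for MBG453. Protocol 6.5.3 does not allow MBG453 dose reductions, so over its own treatment period its RDI would mainly reflect delays and skipped doses. Under the SAP rule it also absorbs permanent discontinuation.

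Partial discontinuation is foreseen by the design: the estimand in SAP 2.5.1 counts one or two of the three drugs as part of the treatment of interest. At stake is the meaning of the RDI figures in the final report, and the fact that they would follow a definition other than the protocol's without saying so.

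**Working it through.** **1. The SAP's own example.** Appendix 5.1 gives a venetoclax example over 4 cycles (112 days), adjusted method:

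- Cumulative dose: 600 + 400×25 + 400×28 + 0×14 + 400×42 = 38,600 mg; 38,600/112×28 = 9,650 mg per 28 days.
- Planned: the same with 400×14 in place of 0×14 = 44,200 mg; 11,050 mg per 28 days.
- RDI = 9,650/11,050 = 87.33%, as stated.

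Side note: the example's ramp-up (100, 200, 300 mg) does not match protocol Table 6-2 (100, 200, then 400 mg from Day 3). The two must be reconciled. On the Table 6-2 figures the RDI would be 38,700/44,300 = 87.36%, so this point is unaffected.

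**2. The SAP rule when one drug stops.** Assume 28-day cycles, full dose D per cycle for k cycles, then a permanent stop, with another drug continuing to cycle n and no delays. Then RDI = (kD/28n)/(D/28) = k/n. The documents give no per-drug stopping data, so k and n are assumptions.

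| Cycles given / regimen cycles | Actual rate per day | Planned rate per day | RDI |
|---|---|---|---|
| MBG453 800 mg, 2/12 | 1,600/336 = 4.762 mg | 28.571 mg | 17% |
| MBG453 800 mg, 6/24 | 4,800/672 = 7.143 mg | 28.571 mg | 25% |
| Azacitidine, 18/30 | 9,450/840 = 11.25 mg/m² | 18.75 mg/m² | 60% |
| Azacitidine, 18/24 | 9,450/672 = 14.06 mg/m² | 18.75 mg/m² | 75% |

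Venetoclax differs from k/n only through its ramp-up (2/12 gives 16%; 18/24 gives 75%).

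**3. Drug-specific exposure.** SAP 5.1 already has component end dates for exposure: last MBG453 dose + 27 days, last azacitidine dose + 20 days, last venetoclax dose.

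- MBG453, six doses: Day 8 to Day 148 + 27 = Day 175, which is 168 days; (4,800/168)/(800/28) = 1.00.
- Azacitidine, two cycles: 55 days if dosing ends on Day 7, 57 if on Day 9; 56/55 = 1.02 or 56/57 = 0.98. More cycles bring this closer to 1.
- Venetoclax: 0.98 (2 cycles) to 1.00 (18 cycles) against the flat 400 mg/day plan.

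**4. Interruption against stopping.** In the SAP's example venetoclax is interrupted for 14 days and resumed. Its own period is still 112 days, so a component-specific denominator leaves 87.33% unchanged. Had it stopped for good after cycle 2 while the other drugs ran to cycle 4, the SAP rule would give 21,800/44,200 = 49%; over its own two cycles it would be 100%.

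**5. Same number, different histories.** SAP 2.4.1 illustrates an RDI of 0.75 with 600 mg on average instead of 800 mg. Full MBG453 dosing for 18 of 24 cycles also gives 0.75.

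**6. Start date of a component-specific period.** MBG453 is first given on Day 8. Counting from that dose to the end of cycle 6 gives 168 − 7 = 161 days and an RDI of 168/161 = 104%. Counting from Day 1 of the first cycle gives 168/168 = 100%.

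**The case against.** The strongest reply is that the SAP rule is a convention, not a mistake. Actual and planned intensity are taken over the same period, so RDI is the share of that drug's planned dose delivered over the whole treated course. For a triplet, stopping one drug early is a failure of delivery, and this version shows it. A component-specific version would give about 100% to a patient who stopped MBG453 after one full dose. This stands: a regimen-wide denominator is usable if it is labelled and declared.

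It is also true that protocol 12.3 does not literally say exposure to that drug. The per-drug reading is an inference, though the natural one given the durations listed earlier in the sentence.

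A reader might infer more than the documents support:

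- *Patients who stop early cannot be told from those who skip doses.* This holds only for RDI read alone. SAP 2.4.1 also summarises exposure duration by component, and interruptions and permanent discontinuations with reasons by component. SAP 2.7.1 tabulates AEs leading to discontinuation of each drug.
- *Discontinuation is counted twice.* Separate descriptive tables are not added together.
- *The longest responders get the worst azacitidine and venetoclax RDI.* RDI depends on k/n: 18 of 30 gives 60%, but 2 of 12 gives 17%. The stop after 18 cycles is also optional.
- *MBG453 RDI is the main measure of whether the triplet can be delivered.* Neither document says so.

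**Conclusion.** The point holds as a limited one. SAP 2.4.1 and 5.1 give all three drugs one regimen-wide denominator. Protocol 12.3, on its natural reading, uses each drug's own exposure, and SAP section 4 does not declare the difference. For any patient who stops one or two drugs and continues the rest, the reported RDI of a stopped drug mixes permanent discontinuation with skipped, delayed or reduced doses.

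The size per patient is k/n: 17% to 75% in the cases shown, against about 100% (0.98 to 1.02) on drug-specific exposure. These figures assume the cycle counts, full dosing until the stop and no delays. The effect on the cohort summaries cannot be estimated from the documents.

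A reader might infer that the trial's main results are at risk. They are not. The CR, EFS, OS and AE analyses do not use RDI, and DLT evaluability in SAP 2.2 rests on counts of doses. Only descriptive exposure summaries change.

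**What to change.** In SAP 2.4.1 and 5.1, report RDI for each component over that component's own period: from Day 1 of the first cycle in which it was given to the end of the last cycle in which it was given. Apply the same period to the planned dose, and keep the existing rule that the duration is not truncated at death or last contact. Start at Day 1 of the cycle rather than at the first administration, for the reason in step 6 of the working. Delays and skipped doses before the drug's last cycle still lower RDI.

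If the current version is wanted, keep it as a second line labelled *relative to duration of the whole regimen*.

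In section 4, replace the present entry with a statement of how both denominators differ from protocol 12.3. The proposed period also differs slightly from the SAP's component exposure dates, which use +27 and +20 days and are cut at death, loss to follow-up or cut-off.

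The cost is SAP wording and component-specific period dates in the exposure program; no new data are needed. The downside is small: the component-specific line says nothing about time after a drug is stopped, so it should be read with the discontinuation table.

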Study treatment consists of cycles of MBG453 (400 mg or 800 mg) administered on Day 8 of each cycle in combination with azacitidine administered intravenous or subcutaneous at 75 mg/m^2 daily during 7 days at the beginning of each cycle (between Day 1 to Day 9 with 3 different regimens possible), and venetoclax administered orally at 400 mg daily or below when administered concomitantly with CYP3A4 inhibitors or P-gp inhibitors (following ramp up starting on Day 1). The planned duration of a cycle is 28 days. Crossover between the different MBG453 doses (400 mg and 800 mg Q4W) is not permitted at any time during the study: subjects included in the first cohort of the safety run-in part will be treated with MBG453 at the 400 mg Q4W dose level during the whole study participation and subjects included in the second cohort of the safety run-in part and in the expansion phase will be treated with MBG453 at the 800 mg Q4W dose level during the whole study participation. Study treatment may continue until the subject experiences disease progression (as defined by ELN 2017 Döhner et al 2017) or unacceptable toxicity.

The first safety review meeting to assess whether MBG453 400 mg Q4W is not meeting overdose criteria (i.e. an excessive incidence of Dose Limiting Toxicities (DLT)) when added

in combination with azacitidine and venetoclax (first cohort of the safety run-in part) will take place after the first 6 subjects treated with MBG453 400 mg Q4W have completed 2 cycles of treatment. If no safety concerned are observed at this dose level, a second safety review meeting to assess whether MBG453 800 mg Q4W is not meeting overdose criteria when added in combination with azacitidine and venetoclax (second cohort of the safety run-in part) will take place after the first 12 subjects treated with MBG453 800 mg Q4W have completed 2 cycles of treatment. Details on the definition of dose limiting toxicities (DLT) are presented in [Table 2-2](#).

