#### **Date of last exposure to study treatment component (MBG453 or azacitidine or venetoclax)**

One planned cycle length is 28 days and the start date of a cycle is defined as the first administration of azacitidine within a cycle. Azacitidine is planned to be administered daily every cycle during 7 days at the beginning of each cycle (between Day 1 to Day 9). MBG453 is administered every 4 weeks (Q4W), on Day 8 of each cycle, unless there was a toxicity leading to a dosing interval increase. Venetoclax is planned to be administered on each day of the 28-day cycle.

The date of last exposure to MBG453 is therefore calculated as:

- Minimum (last date of administration of MBG453 + 27 days, date of death, last contact date in case subject is lost to follow-up, analysis cut-off date), as MBG453 injections are given Q4W.

The date of last exposure to azacitidine is calculated as:

- Minimum (last date of administration of azacitidine + 20 days, date of death, last contact date in case subject is lost to follow-up, analysis cut-off date) as the 7 doses of azacitidine are given in the beginning of each cycle.

The date of last exposure to venetoclax is calculated as:

- Minimum (the date of last administration of a non-zero dose of venetoclax, date of death, last contact date in case subject is lost to follow-up, analysis cut-off date), as venetoclax is given in a daily administration (in case of regimen change to “three weeks on, one week off”, the cycle would end after 7 days; in case of regimen change to “two weeks on, two week off”, the cycle would end after 14 days; in case of regimen change to “one week on, three week off”, the cycle would end after 21 days).

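### SAP 2.4.1 equates an azacitidine planned dose intensity of 75 mg/m² per day with 525 mg/m² per 28 days; by the SAP's own definition these differ four-fold, and only 525 is correct

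*SAP*

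**What the plan says.** SAP 2.4.1, under the heading on dose intensity and relative dose intensity, gives three definitions:

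- Actual dose intensity is "computed as the ratio of actual cumulative dose received and duration in days from first to last cycle initiated".
- Planned dose intensity "is the ratio of planned cumulative dose and duration in days from first to last cycle initiated".
- For the comparison of the two: "The relative dose intensity is then computed as the ratio of actual dose intensity and planned dose intensity".

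It then lists planned values by drug:

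- MBG453: 400 mg or 800 mg per 28 days. No per-day value is given.
- Azacitidine: "For azacitidine, the planned dose intensity is 75 mg/m"² per day, "which is equivalent to 525 mg/m"² per 28 days. (Both quotes break off at the superscript.)
- Venetoclax: 400 mg per day, stated to equal 11,200 mg per 28 days.

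SAP Appendix 5.1 fixes the duration. It runs from the first administration of study treatment to the end of the last cycle initiated, and that end is never earlier than Day 28 of the cycle. The divisor is therefore calendar days, not dosing days.

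On the schedule, Appendix 5.1 says "Azacitidine is planned to be administered daily every cycle during 7 days at the beginning of each cycle", and SAP 1.1 says "The planned duration of a cycle is 28 days".

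**The concern.** The sentence offers two azacitidine figures as the same quantity. Under the definition a few lines above them they are not. Nothing in the section limits the per-day unit to dosing days, and the venetoclax line directly below uses the same form of words for every calendar day. One unit therefore carries two meanings in adjacent lines.

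The units add to the risk. Azacitidine cumulative dose is in mg/m², and the written formula for actual dose intensity divides it by a number of days, with no rescaling to 28 days. Taken literally, the actual value comes out in mg/m² per day. The planned figure in that unit is 75, which is the wrong one of the two.

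At stake is the denominator of azacitidine relative dose intensity. That quantity is summarised for each treatment component under SAP 2.4.1 and Protocol 12.3, and it appears in the list of safety review outputs in SAP 2.10.

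**Working it through.** **Inputs**

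- Dose on an administration day: 75 mg/m² (SAP 1.1; Protocol 6.1.1)
- Administration days per cycle: 7 (SAP 1.1 and Appendix 5.1)
- Planned cycle length: 28 days (SAP 1.1)
- Divisor: calendar days from first to last cycle initiated (SAP 2.4.1 and Appendix 5.1)

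**Step 1. Reproduce the SAP's figures.** Planned cumulative dose per cycle = 75 × 7 = 525 mg/m², so 525 mg/m² per 28 days is reproduced. Read as a rate over the defined duration, 75 mg/m² per day gives 75 × 28 = 2,100 mg/m² per 28 days, and 2,100/525 = 4. The stated equivalence is not reproduced.

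**Step 2. Apply the definition per day.** Planned dose intensity = 525/28 = 18.75 mg/m² per day. Against the stated 75, the ratio is 75/18.75 = 4.

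**Step 3. Check the neighbouring line.** For venetoclax, 400 × 28 = 11,200 mg per 28 days. That equivalence holds on calendar days.

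**Step 4. Effect on relative dose intensity.** Take a subject who receives all 7 doses of 75 mg/m² in each of *c* cycles of 28 days. Actual dose intensity = 525*c* / 28*c* = 18.75 mg/m² per day, whatever the value of *c*.

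| Planned value used as denominator | Relative dose intensity |
|---|---|
| 75 mg/m² per day | 18.75/75 = 25% |
| 18.75 mg/m² per day (= 525 per 28 days) | 18.75/18.75 = 100% |

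For any other subject with actual dose intensity *A* per day, the two results are *A*/75 and *A*/18.75. The first is always one quarter of the second.

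**Step 5. Which scale do the other two drugs use?** The MBG453 planned value is given only per 28 days, and its illustration compares 600 mg with 800 mg every 4 weeks (600/800 = 0.75). The venetoclax worked example in Appendix 5.1 rescales the actual value: 30,200/(28 × 4) × 28 = 7,550 mg per 28 days unadjusted, and 38,600/(28 × 4) × 28 = 9,650 mg per 28 days adjusted. It divides the adjusted value by a planned value of 11,050 mg per 28 days to get 87.33%. Both drugs point to a 28-day scale. Azacitidine has no worked example.

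**The case against.** The strongest reply is that the intended meaning is plain. The number 525 can only come from 75 × 7, so 75 mg/m² per day must be shorthand for the dose on an administration day. The correct denominator stands in the same sentence, and the general definition reproduces it without using the per-day figure. The 28-day scale is the only one given for all three drugs, and the venetoclax example rescales both actual and planned values to it. A program that capped fully dosed subjects at 25% would be conspicuous in the output.

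Most of this stands. It shows what was meant and makes a programming error unlikely. It does not make the stated equivalence true, and the 28-day scale reaches azacitidine only by analogy, because the written formula for actual dose intensity is per day and no text rescales it for this drug.

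A reader might infer more than the documents support in two ways:

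- **That azacitidine relative dose intensity will be, or has been, reported at a quarter of its true value.** Nothing in the documents shows that 75 was programmed as the denominator.
- **That safety decisions are affected, because one DLT criterion also refers to planned dose intensity.** DLTs rest on investigator assessment and are captured on the adverse event form. No text ties that criterion to the variable derived in SAP 2.4.1. DLT evaluability counts doses (11 of 14 for azacitidine), and the overdose rule uses the posterior DLT probability.

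**Conclusion.** The point holds as a wrong figure in an analysis rule. As a dose intensity under the SAP's definition, 75 mg/m² per day is four times too large. The correct value is 525 mg/m² per 28 days, which equals 18.75 mg/m² per day averaged over the cycle.

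The fall from 100% to 25% is conditional: it occurs only if the per-day figure is used as the denominator against an actual dose intensity per day. It also assumes full dosing and 28-day cycles; the four-fold factor itself does not depend on either.

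The consequence is limited to a descriptive exposure summary. The CR decision rule and the secondary efficacy endpoints do not use relative dose intensity. The point is minor, but worth correcting because the figure defines a reported quantity.

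**What to change.** In SAP 2.4.1:

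1. State the azacitidine planned dose intensity as 525 mg/m² per 28 days, with the derivation: 75 mg/m² per dosing day × 7 days, or 18.75 mg/m² per day averaged over the cycle.
2. State that actual and planned dose intensity are both expressed per 28 days for all three drugs, as in the venetoclax example in Appendix 5.1.
3. Confirm that the azacitidine program uses 525 mg/m² per 28 days as the denominator.

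The cost is a line or two of SAP text and one program check. The change restates the existing schedule and alters no dosing instruction.
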